#### **9.1.3 Other Parameters Specific to Study Design**

##### **9.1.3.1 Injection Site Reactions**

Mild or moderate local reactions at the injection site are expected. Patients are likely to experience a skin reaction and some discomfort around the injection site [1]. Each patient will be given general and written advice regarding the management of local injection site reactions and generalised systemic symptoms (e.g., pyrexia, headache and general malaise). Where symptoms persist or result in functional limitations, patients will be advised to attend the next possible research clinic or see their own GP.

Before each administration of IMM-101, the injection site must be inspected for local reaction(s). In addition, patients will be asked to assess their injection site reaction, and its effect on their daily activities:

"Has the local reaction affected your daily activities?"

- Not at all
- Slightly
- Moderately
- Quite badly
- Intolerably

Although a formal assessment is performed before each injection, an injection site reaction may be recorded as an AE at any time if considered appropriate to do so by the Investigator.

In the event of an injection site reaction of Grade 3 (severe) as measured by the NCI CTCAE v4.0 and above, at the discretion of the Investigator, patients may be administered a half dose of the study drug (i.e., a single 0.05 mL intradermal injection of IMM-101) or the time interval between injections of IMM-101 may be extended. Any change in the dose of study drug administered should be recorded in the patient's CRF.

If dosing is discontinued or the patient withdraws from the study as a result of an intolerable injection site reaction, this must be recorded in the CRF.

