### **9.2 *ASSESSING, RECORDING AND ANALYSING SAFETY PARAMETERS***

Adverse events will be recorded on the patient's CRF from the time of informed consent (i.e., screening). AEs will be followed until 30 days after the end of study/withdrawal. The Investigator may contact the patient by telephone to obtain the information. See Section 0 for further details. Related SAEs will be recorded regardless of time from last dose.

Injection site reactions will be assessed and recorded in the patient's CRF before each injection of study drug. These will only be recorded as an AE if deemed appropriate by the Investigator. In addition, the patient's assessment of the effect of the injection site reaction on their daily activities will be recorded at each visit, as described in Section 9.1.3.1.

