##### Local and Systemic Toxicities

Local and systemic toxicities will be presented over the treatment period in standard frequency tables overall and by number, degree and type.

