#### 10.1.1.2 *Other Safety Endpoints*

##### Injection Site Reactions

The frequency and severity of injection site reactions will be summarised.

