4. PLANNED ANALYSES

At the time of final analysis for the study, descriptive summaries of the results of the study will be provided along with data listings of the final study database. Summary statistics or frequency tables will be provided, where appropriate.

Section 9 provides details of the descriptive statistics and TFL shells are included in Section 13.

No formal statistical analyses of the results are anticipated and hence no statistical inferences will be made.

Planned analyses as detailed in the protocol are as follows:

The evaluation of safety and tolerability will be summarised using the Safety population and will be based on local and systemic toxicities (including injection site tolerability) which will be presented over the treatment period in standard frequency tables, overall and by number, degree and type. Adverse Events will

be presented descriptively to include related adverse events, serious adverse events (SAEs), and adverse events leading to withdrawal or death. The frequency and severity of injection site reactions, and all other safety parameters will be summarised.

All patients will have received IMM-101 in the context of both the Phase 1 study and, for the majority, on a Named Patient basis; therefore all AEs in this long term follow up study will be regarded as treatment emergent.

Efficacy will be presented using the Safety population and will be assessed through documenting the long-term clinical course of the patients previously enrolled in Study IMM-101-001 in terms of OS. Reduction in metastatic disease will be listed only.

Variables for the exploratory endpoints will be analysed and reported separately to the main efficacy and safety endpoints of the study.

The protocol specified that OS will be presented from enrolment into this study, in addition to time from initial diagnosis and enrolment into study IMM-101-001. Time zero for the OS analysis in this study (IMM-101-008) will be based on the date of Day 0 in this study and analysis of OS taking into account time from initial diagnosis and first dosing day in Study IMM-101-001 will not be included in this SAP as not all patients completing the FIH study entered the LTF study.

In addition to the above planned presentations, non-serious adverse events in LTF study patients will be tabulated and treatment-related treatment emergent AEs will also be presented combining data in these patients, from both the FIH and LTF studies.

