- Treatment emergent, IMM-101-related, adverse events: AEs that are definitely, probably or possibly related to study drug or with an unknown relationship (Table 10d)
- Treatment emergent, SAEs (Table 10e)
- Treatment emergent adverse events leading to withdrawal or death (Table 10f).
- Treatment emergent non-serious adverse events (Table 10g).

Additionally, long term safety will be evaluated by combining treatment related adverse event experience in the FIH study through to the end of the LTF study by summarising treatment emergent treatment-related adverse events (IMM-101-001 and IMM-101-008 Combined) (Table 10h).

Where it is not applicable to grade an AE using NCI CTCAE grade, it will be excluded from the summary of NCI Grade 3 and above AEs. Any AEs with missing grades, however, will be included, based on a worst-case approach.

On-study injection site reactions are summarised over the treatment period by visit in Table 11.

Urine Pregnancy Test Results and blood samples for immunological markers will be listed but not summarised.

All safety data will be listed.

Any comments recorded as free text in the CRF will be listed.

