Total Number of treatment-related treatment emergent adverse events	xx
System Organ Class	n (xx.x) m
Preferred Term	n (xx.x) m

Note: n = number of patients with an AE; m = number of AEs.

Hence if a patient has multiple AEs only one occurrence per person will contribute to 'n', but all occurrences will be counted under 'm' as this is the total number of events recorded.

Note: Preferred Term and System Organ Class are coded using MedDRA version 18.1.

Note: Percent is based on the total number of patients in the Safety Population.

Note: Treatment emergent AEs are all those reported at/after first IMM-101 dosing in study IMM-101-001. Related AEs are defined as AEs that are definitely, probably or possibly related to study drug or with an unknown relationship.

Code: S:\Services\Immodulon\IMM-101-008\Analysis\Development\Code\ Table10h.sas ddmmmyy:hh:mm:ss

Data: S:\Services\Immodulon\IMM-101-008\xxxxx.sas7bdat

Data: S:\Services\Immodulon\IMM-101-001\xxxxx.sas7bdat

Note to programmer: Please update data footnote with appropriate file directory.**Note to Programmer:** Order by most common (by incidence) SOC and PT within SOC.

CONFIDENTIAL

Exploristics Limited

Identifier: EXP12002

Clinical Study Identifier: IMM-101-008

Final Analysis

Protocol: IMM-101-008

Analysis Population: Safety Population

Page x of y

Table 11
On-Study Injection Site Reaction(s)

	Visit 1 N = xx (%)	Visit 2 N = xx (%)	Visit N N = xx (%)
Is the injection site reaction from previous IMM-101 dose(s) visible?	N	N	N
Yes	xx (xx.x)	xx (xx.x)	xx (xx.x)
No	xx (xx.x)	xx (xx.x)	xx (xx.x)
If visible, are daily activities affected?	N	N	N
Not at all	xx (xx.x)	xx (xx.x)	xx (xx.x)
Slightly	xx (xx.x)	xx (xx.x)	xx (xx.x)
Moderately	xx (xx.x)	xx (xx.x)	xx (xx.x)
Quite badly	xx (xx.x)	xx (xx.x)	xx (xx.x)
Intolerably	xx (xx.x)	xx (xx.x)	xx (xx.x)
Worsening with repeated doses of IMM-101?	N	N	N
Yes	xx (xx.x)	xx (xx.x)	xx (xx.x)
No	xx (xx.x)	xx (xx.x)	xx (xx.x)
Not Sure	xx (xx.x)	xx (xx.x)	xx (xx.x)
Wound care required?	N	N	N
Yes	xx (xx.x)	xx (xx.x)	xx (xx.x)
No	xx (xx.x)	xx (xx.x)	xx (xx.x)

Note: Percent are based on the number of patients available at each visit who provided a response.

Code: S:\Services\Immodulon\IMM-101-008\Analysis\Development\Code\Table11.sas ddmmmyy:hh:mm:ss

Data: S:\Services\Immodulon\IMM-101-008\xxxxx.sas7bdat

Note to programmer: Please update data footnote with appropriate file directory.

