Note to programmer: Where 'Visit N' appears add additional columns as required, or reverse rows and columns if visits large in number, so rows become visits and variables are in the columns.

CONFIDENTIAL

Exploristics Limited

Identifier: EXP12002

Clinical Study Identifier: IMM-101-008

Final Analysis

Protocol: IMM-101-008

Page x of y

Analysis Population: Safety Population

Listing 1
Patient Disposition

Unique Patient ID	Consent Date (DD-MM-YYYYTHH:MM)	Version Number	Off-Study Date (DD-MM-YYYY)	Off-Study Status	Time on Study (years)	Overall Study drug exposure (months)	Total no. IMM-101 Doses received on Study	Reason for Completion (death) or Withdrawal	All adverse events followed for at least 30 days after study completion/withdrawal	Principal Investigator Sign off Date (DD-MM-YYYY)
xxxxxx	DD-MM-YYYY HH:MM	xx	DD-MM-YYYY	xxxxxx	xx	xx	xx	xxxxxx	xxxxxx	DD-MM-YYYY
xxxxxx	DD-MM-YYYY HH:MM	xx	DD-MM-YYYY	xxxxxx	xx	xx	xx	xxxxxx	xxxxxx	DD-MM-YYYY
xxxxxx	DD-MM-YYYY HH:MM	xx	DD-MM-YYYY	xxxxxx	xx	xx	xx	xxxxxx	xxxxxx	DD-MM-YYYY
xxxxxx	DD-MM-YYYY HH:MM	xx	DD-MM-YYYY	xxxxxx	xx	xx	xx	xxxxxx	xxxxxx	DD-MM-YYYY
xxxxxx	DD-MM-YYYY HH:MM	xx	DD-MM-YYYY	xxxxxx	xx	xx	xx	xxxxxx	xxxxxx	DD-MM-YYYY
xxxxxx	DD-MM-YYYY HH:MM	xx	DD-MM-YYYY	xxxxxx	xx	xx	xx	xxxxxx	xxxxxx	DD-MM-YYYY

Note: Time on study (years) = (date of completion (i.e. death on study)/date of withdrawal - Day 0 + 1)/365.25.

Overall Exposure (months) = (date of last dose - date of first dose in study IMM-101-008 + 1)/30.4375.

Total number of doses received = sum of the doses (full or part doses counted as 1 dose) received, as reported in the CRF.

Note: The trial was terminated in Dec-2018 as no further meaningful data was being collected nor was likely to be collected in the future.

Code: S:\Services\Immodulon\IMM-101-008\Analysis\Development\Code\Listing1.sas ddmmmyy:hh:mm:ss

Data: S:\Services\Immodulon\IMM-101-008\xxxxxx.sas7bdat

Note to programmer: Please update data footnote with appropriate file directory.**Note to programmer:** Off-Study Status should be either 'Completed Study - patient died' or 'Withdraw'.**Note to Programmer:** Where applicable, separate date from time using a space.**Note to Programmer:** Status at completion/withdrawal: If reason is AE/unacceptable toxicity, Investigator decision or Patient did not meet INC/EXC criteria, please include specify text. If reason is other please include reason/description where applicable.

CONFIDENTIAL

Exploristics Limited

Identifier: EXP12002

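### Injection site reactions are promised in overall frequency tables, but Table 11 reports them by visit only, so no table counts the patients ever affected or their worst level

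*SAP*

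**What the plan says.** Local injection site tolerability is the first safety and tolerability endpoint in SAP 2.2. Protocol 10.1.1.1 states: "Local and systemic toxicities will be presented over the treatment period in standard frequency tables overall and by number, degree and type". Protocol 10.1.1.2 adds: "The frequency and severity of injection site reactions will be summarised". SAP section 4 repeats the plan and names this endpoint within it: "local and systemic toxicities (including injection site tolerability) which will be presented over the treatment period in standard frequency tables, overall", then the same breakdown as the protocol.

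The output specification is narrower. SAP 9.3 says: "On-study injection site reactions are summarised over the treatment period by visit in Table 11". The Table 11 shell has one column per visit and four items: whether a reaction is visible, its effect on daily activities, worsening with repeated doses, and wound care. Its footnote sets the denominator: "Percent are based on the number of patients available at each visit who provided a response". The programmer note allows more visit columns, or says to "reverse rows and columns if visits large in number". Neither option adds a figure across visits.

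On the route into the adverse event data, Protocol 9.2 says of injection site reactions: "These will only be recorded as an AE if deemed appropriate by the Investigator". Protocol 9.1.3.1 likewise says "an injection site reaction may be recorded as an AE at any time if considered appropriate to do so by the Investigator".

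**The concern.** The study exists to describe safety on extended dosing, and Protocol 3.4 names injection site reactions as the main risk. Two questions follow. Do reactions change as doses accumulate? How many of the treated patients were affected, and how badly at worst? Table 11 is a sensible display for the first question. It cannot answer the second, because each column is a separate snapshot of whoever attended and responded. A reaction that persists is counted at several visits, so the columns cannot be added up to a number of patients. A report built on these shells could not say, from any table, whether troublesome reactions fell repeatedly on one patient or once each on many.

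**Working it through.** The documents give no figure to reproduce: Protocol 10.2 and 10.3 are marked not applicable and the analysis is descriptive. The check has two parts.

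**Does any other table give the patient-level figure?**

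- Table 5 covers reactions present at screening and the pre-study history of severe local reactions. It does not cover the study period.
- Table 7 gives full or reduced doses by visit. It does not describe reactions.
- Tables 10a to 10h count each patient once on the Safety Population, and Table 10c does so for Grade 3 or above. They contain only reactions entered as adverse events at the Investigator's discretion, and they carry no daily-activities level. The visit check shown in Listing 14 asks about signs and symptoms other than a local reaction.
- Listing 13 holds each patient's answers at every visit, but nothing is derived from it across visits.

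So no table supplies it.

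**How much do by-visit counts leave open?**

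Take any yes/no condition in Table 11. Let N be the number of patients, V the number of visits, and k the number affected at each visit, with everyone attending and responding. The number ever affected, D, satisfies

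k ≤ D ≤ min(N, kV).

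The lower limit applies when the same patients are affected each time, the upper when they differ as much as possible. If the count varies, with k_v affected at visit v, the limits are the largest k_v and min(N, sum of the k_v).

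N is not stated, so two values are assumed:

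- N = 10, from the 2x5 panel layout in the Figure 1a shell.
- N = 12, from Protocol 4.2: 18 − 3 − 1 − 2 = 12.

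With k = 1 in the visible-reaction row, whose denominator is all responders at the visit:

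| N | V | Every column shows | Limits for D | Share ever affected |
|---|---|---|---|---|
| 10 | 6 | 1/10 = 10.0% | 1 to 6 | 10% to 60% |
| 12 | 6 | 1/12 = 8.3% | 1 to 6 | 8.3% to 50% |
| 10 | 24 | 10.0% | 1 to 10 | 10% to 100% |
| 12 | 24 | 8.3% | 1 to 12 | 8.3% to 100% |

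To see what lies between the limits, suppose the affected patient is the same as at the previous visit with probability r, and otherwise is any of the other N − 1 with equal chance. Then

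E(D) = N − (N − 1) × [1 − (1 − r)/(N − 1)]^(V − 1).

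For V = 6:

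- N = 10, r = 0.9: 10 − 9 × (1 − 0.1/9)^5 = 1.49, or 14.9%.
- N = 10, r = 0.5: 10 − 9 × (1 − 0.5/9)^5 = 3.24, or 32.4%.
- N = 10, a random patient each visit: 1 − (1 − 1/10)^6 = 46.9%.
- N = 12, the same three cases: 12.4%, 27.4% and 40.7%.

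All the cases for a given N print the same Table 11 row.

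The table could be long. From the first protocol version (15 September 2011) to termination in December 2018 is 2,634 days if 1 December is used. Since 2,634/28 = 94.07, that allows at most about 94 nominal four-weekly visits.

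**The case against.** The strongest reply is that little is lost. The study is descriptive, all safety data are listed, and with some 10 to 12 patients a reader could tally Listing 13 by hand. Table 11 bears directly on the protocol's stated worry that reactions may increase with repeated dosing, and it asks about worsening. Reactions are expected, so the visible row may sit near its ceiling; a column reading 10 of 10 would settle the ever-affected count at once. The daily-activities rows apply only to visible reactions and have their own denominator, so the percentages above do not carry over to them. All of this stands and limits the size of the point. It does not supply the overall figure, and the bounds on counts still apply to the less common outcomes, such as the worse daily-activities levels and wound care.

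It can also be argued that the adverse event tables fulfil the promise. They do so for reactions entered as adverse events, which is a discretionary subset.

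A reader might infer several stronger points that the documents do not support:

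- *The plan fails to deliver a promised table of dose changes caused by reactions.* No section promises one, and Figure 1a plots every on-study dose for each patient, so reductions and gaps are visible. Only the reason is confined to Listing 10.
- *There is no on-study count of severe reactions.* Table 10c gives a partial one.
- *The conditional daily-activities row discards answers about reactions that had resolved.* That depends on the CRF, which is not among the documents.
- *CTCAE grades for local reactions go unreported.* Protocol 9.1.1.4 requires grading only where applicable, and Table 10c and Listing 12 report grades for adverse events.

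**Conclusion.** The point holds as a mismatch between what SAP section 4 and Protocol 10.1.1.1 plan and what SAP 9.3 and Table 11 specify for a named safety endpoint. No table gives the number of treated patients with an on-study reaction or their worst daily-activities level. Identical by-visit output can correspond to very different patient-level pictures. The bounds need only the attendance and response condition stated with them. The percentages also rest on assumed values of N, V and k, and the intermediate ones on an assumed r; they illustrate the ambiguity and do not predict this study's results. The gap is worth correcting because it affects what can be concluded about tolerability, but the underlying data remain available in the listings.

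**What to change.** Keep the by-visit display. Add an overall column to Table 11 (or an overall row, if transposed), with the Safety Population as denominator and restricted to visits after Day 0, since the Day 0 check in Protocol 5.2.1.2 concerns pre-existing reactions. Show n (%) of patients with:

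1. any visible reaction;
2. each daily-activities level as the worst recorded;
3. worsening reported at any visit;
4. wound care required at any visit;
5. no response after Day 0.

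Add a footnote that worst-ever figures rise with length of follow-up and should be read beside the by-visit columns and the exposure summary in Table 9a. Amend SAP 9.3 to match.

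As an optional addition, which the plan does not promise, include a row for patients with at least one dose reduction or delay attributed to an injection site reaction, taken from the reason field in Listing 10.

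The cost is minor programming from data already in Listing 13, plus a review of free-text reasons if the optional row is used. No new data are needed, and the change concerns reporting only, not any dosing rule.

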8.3 Derived and Transformed Data

As age was not collected it will be derived using the patient's date of birth and date of consent. The derivation will be

Age (years) = integer part of ((patient informed consent date - date of birth + 1)/365.25).

Note that the full date of birth will be used in the calculation, but only year of birth will be listed. Patient initials will not be listed.

Time since initial diagnosis of current presentation, time since excision of primary lesion, time since excision of sentinel node and time since regional lymph node resection will be derived in years as follows;

Time since initial diagnosis of current presentation (years) = (Day 0 - date of initial diagnosis of current presentation + 1) / 365.25

Time since excision of primary lesion (years) = (Day 0 - date of excision of primary lesion + 1) / 365.25.

Time since excision of sentinel node (years) = (Day 0 - date of excision of sentinel node + 1) / 365.25 and missing if not excised.

Time since regional lymph node resection (years) = (Day 0 - date of regional lymph node resection + 1) / 365.25 and missing if not resected.

The relevant time variable above will be reported to 1 decimal place, but calculated using all accuracy available in the data. If any dates are partial, i.e. day number missing, the time variable will be calculated using month and year only and if day and month missing, the time variable will be calculated using year only as follows:

- If only month and year are present (MMYYYY): Time since Event = (Day 0 – Event date +1) / 365.25;
- If only year is present (YYYY): Time since Event = (Day 0 – Event date) +1 / 365.25.

The total number of pre-study doses of IMM-101 received (since the completion of study IMM-101-001) will be calculated for each patient.

Exposure during the IMM-101-008 study will be summarised by time on study in years and overall exposure in months, which will be derived using:

Time on study (years) = (date of study completion (i.e. death on study)/date of withdrawal) - Day 0 + 1) / 365.25.

Overall study drug exposure (months) = (date of last dose - date of first dose in study IMM-101-008 + 1) / 30.4375.

Overall exposure of IMM-101 (FIH and LTF study combined) will be derived using:
(date of last dose in study IMM-101-008 – date of first dose in study IMM-101-001 + 1) / 30.4375.

On-study dosing will be summarised using the total number of doses on study:

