9. DESCRIPTIVE STATISTICS

9.1 Disposition of Patients

The number and percentage of patients meeting all inclusion criteria, completing (i.e. dying) and withdrawing will be summarised (Table 1), along with reasons for death and withdrawal from study.

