13.2 Data Display Specification

Final Analysis

Protocol: IMM-101-008

Analysis Population: All patients

Page x of y

Table 1
Summary of Patient Disposition

	N = xx	(%)
Number of patients who entered the study	xx	
Number of patients in the safety population	xx	(xx.x)
Number of patients who met all Inclusion/Exclusion criteria	xx	(xx.x)
Number of patients who died on study	xx	(xx.x)
Reason for death		
Adverse event/unacceptable toxicity	xx	(xx.x)
Other: Death due to disease progression	xx	(xx.x)
Number of patients who withdrew from the study	xx	(xx.x)
Reason for Withdrawal		
Adverse event/unacceptable toxicity	xx	(xx.x)
Patient request/withdrawal of consent	xx	(xx.x)
Investigator decision	xx	(xx.x)
Did not meet inclusion/exclusion criteria	xx	(xx.x)
Pregnancy	xx	(xx.x)
Non-compliant	xx	(xx.x)
Other	xx	(xx.x)

Note: Percent is based on the total number of patients in the Safety Population.

Code: S:\Services\Immodulon\IMM-101-008\Analysis\Development\Code\Table1.sas ddmmmyy:hh:mm:ss

Data: S:\Services\Immodulon\IMM-101-008\xxxxx.sas7bdat

Note to programmer: Please update data footnote with appropriate file directory.

Note to programmer: Completion date is date of death. Death reasons are recorded in categories stated.

Note to programmer: The number of patients who met all Inclusion/Exclusion criteria is based on response from page 12 of the CRF

CONFIDENTIAL**Exploristics Limited**

Identifier: EXP12002

Clinical Study Identifier: IMM-101-008

Final Analysis

Protocol: IMM-101-008

Analysis Population: Safety Population

Page x of y

Table 2
Demographics

N = xx (%)

Age at informed consent (yrs)

N	xx
Mean	xx.x
SD	xx.xx
Median	xx.x
Min.	xx
Max.	xx

Gender (%)

N	
Female	xx (xx.x)
Male	xx (xx.x)

If Female: Child-bearing status (%)

N	
Post-menopausal	xx (xx.x)
Surgically sterile	xx (xx.x)
Childbearing potential	xx (xx.x)
Unknown	xx (xx.x)

Race/ethnicity (%)

N	
Black/Afro-Caribbean	xx (xx.x)

CONFIDENTIAL**Exploristics Limited**

Identifier: EXP12002

Clinical Study Identifier: IMM-101-008

White/Caucasian	xx (xx.x)
Asian	xx (xx.x)
Other	xx (xx.x)

Height (cm)	
N	xx
Mean	xx.x
SD	xx.xx
Median	xx.x
Min.	xx
Max.	xx

WHO performance status (%)	N
0	xx (xx.x)
1	xx (xx.x)
2	xx (xx.x)
3	xx (xx.x)
4	xx (xx.x)

CONFIDENTIAL

Exploristics Limited

Identifier: EXP12002

Clinical Study Identifier: IMM-101-008

Note: Percent is based on the number of patients who provided a response for each criteria.

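### Does the lack of a study-termination category in SAP Table 1 and Listing 1 misstate patient disposition?

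*SAP*

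**What the plan says.** SAP 9.1 describes disposition with two outcomes: patients "completing (i.e. dying) and withdrawing will be summarised (Table 1), along with reasons for death and withdrawal from study". The shells in SAP 13.2 follow this. Table 1 has a row for deaths on study and a row headed "Number of patients who withdrew from the study", with seven reasons beneath the latter. For Listing 1 the programmer is told that "Off-Study Status should be either 'Completed Study - patient died' or 'Withdraw".

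The footnote to Listing 1 states: "The trial was terminated in Dec-2018 as no further meaningful data was being collected nor was likely to be collected in the future". A further note on the reason column says: "If reason is other please include reason/description where applicable".

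The time-on-study formula in SAP 8.3 ends at the "date of study completion (i.e. death on study)/date of withdrawal", so it too names only two kinds of exit.

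Table 1 is headed "Analysis Population: All patients", while its footnote reads "Percent is based on the total number of patients in the Safety Population".

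**The concern.** SAP Amendment 1 took effect on 10 April 2019, after the trial had closed, and its authors knew of the closure because they footnoted it. Even so, neither shell has a place for a patient who neither died nor chose to leave but was on study when it stopped. Such a patient can only be listed as a withdrawal.

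The protocol does mention termination apart from withdrawal. Section 5.4 names it as a separate limit on continued treatment, 6.4.2 gives it its own heading, and 6.5 distinguishes patients leaving from the study ending. Long-term safety is the first objective, so a reader may want to know how many patients stayed to the end. If closure exits are pooled with withdrawals, Table 1 alone could understate retention. The mismatch between the table's heading and its percentage base looks like a second slip in the same shell.

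**Working it through.** The documents state no figure on this point, so there is none to reproduce. The check compares the texts, with one small illustration of size.

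**1. What the shells offer.** The Table 1 withdrawal reasons are adverse event or toxicity, patient request, investigator decision, eligibility failure, pregnancy, non-compliance and *Other*. That makes 7, of which none names termination and one is a catch-all. Listing 1 has 2 status values, and neither names termination. A patient on study at closure therefore goes to the withdrawal row, most plausibly under *Other*.

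**2. Timing.** From 31 December 2018 to 10 April 2019 is 31 + 28 + 31 + 10 = 100 days. From 1 December it is 30 days more, or 130. The authors wrote with the closure behind them. They may also have known every patient's exit status by then; the documents do not settle this.

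**3. Is the label permitted?** Protocol 6.3.1 allows withdrawal at the Sponsor's discretion and lists administrative problems among the exit reasons. The protocol synopsis and SAP Section 1 both frame participation as running to death or withdrawal. Sections 6.4.2 and 6.5 deal with who may stop the study, what must then be done, and standard care afterwards. Section 5.4 deals with how long treatment may continue. None of them sets reporting categories.

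**4. Is the reason lost?** No. Listing 1 shows each patient's off-study date, status and reason, asks for the text when the reason is *Other*, and carries the termination footnote.

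**5. Does any result change?**

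- *Overall survival.* Under SAP Section 10 a living patient is censored at withdrawal, or at a later date last known alive where consent was given. The patient is censored whichever label is used.
- *Time on study.* A closure patient coded as withdrawn has an off-study date, so the SAP 8.3 formula gives (off-study date − Day 0 + 1)/365.25. An undefined end date would arise only if a third status were created.
- *Adverse events.* Protocol 9.2 sets the same 30-day follow-up after end of study and after withdrawal. Nothing in the documents shows that these tables depend on the disposition label.

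**6. Size in Table 1.** Each patient on study at closure adds 1/N to the withdrawal percentage. N is not given, so three assumed values are used:

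| Assumed N | Basis | 1/N |
|---|---|---|
| 10 | the 2x5 panel layout for Figure 1a | 10.0 points |
| 12 | 18 eligible − 6 stopped by August 2011 (protocol 4.2) | 8.3 points |
| 16 | 19 enrolled − 3 deaths, an upper bound (protocol 3.3, 4.2) | 6.3 points |

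If nobody was on study at closure, the effect is zero.

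**7. Heading and denominator.** The first row of Table 1 counts everyone who entered and carries no percentage, which explains the all-patients heading. The percentage base is stated in a note. The two populations differ only if someone entered and was never dosed in this study. No document says that happened, and if it did, the counts in the first two rows would show it.

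**The case for a change.** The best argument for acting is that *Other* is a poor home for closure. Protocol 6.3.1 also lists loss to follow-up, and Table 1 has no row for that either. One row could therefore pool genuine attrition with patients who stayed to the end. In a long-term safety study that is a distinction a disposition table would normally draw. With so few patients, one case moves the percentage visibly. The cost would be one line in a shell, and a zero in that line would itself be informative.

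Most of this is fair as a matter of layout. Table 1 read alone cannot separate the two, and a separate reason row would be harmless. But the argument shows only that Table 1 could be more convenient, not that it would be wrong or that information would be lost. At most 16 patients on the assumption above can be reconciled against Listing 1 by eye. Retention is not an endpoint, there is no comparator, and SAP Section 4 rules out inference. Duration is summarised separately in Table 9a.

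**Conclusion.** The texts do read as described: the shells have two exits, and the SAP records a termination that fits neither by name. No change to the plan follows. The label is one the protocol allows, the true reason is listed patient by patient, and the survival and time-on-study results are the same either way. The possible effect is confined to one count and percentage in Table 1, at 1/N per patient, or about 6.3 to 10.0 points on the assumed N, and it is nil if nobody was on study at closure. The mixed population heading is immaterial unless a patient entered and was never dosed.

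This rests on two assumptions: that the off-study page was completed with a date and reason for every patient, which Listing 1 takes for granted, and that the study remains descriptive, as both documents say.
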